## 9. DATA COLLECTION

### 9.1. CONSTRUCTS AND MEASURES

*Clearly articulate the constructs of interest, measures to evaluate those constructs, and specific data collection instruments. Provide any information on the reliability and validity of the data collection instruments. For standardized instruments, you may provide the citation for the instrument.*

Construct	Measure	Instrument	Reliability and Validity (if standardized instrument, you provide a citation for the instrument)
Parenting Behavior (interaction with children)	1 item: hours spent w/children in last 30 days (interval); 1 item: frequency reach out to children (categories, 5-point scale); 7 items: frequency engage in key behaviors (categories, 5-point scale)	nFORM Community-Based Fathers Survey (A2b, A2c, A5b: b-d, f-i)  *also asked on OLLE; will use data from survey with the most complete data	n/a

Co-Parenting Behavior	11 items: frequency of agreement with key co-parenting behaviors (interval, 5-point scale)	nFORM Community-Based Fathers Survey (A13: a-k)  *also asked on OLLE; will use data from survey with the most complete data	n/a
Father Financial Behavior	2 items: yes or no questions for have resume, checking/savings accounts (dichotomous)	nFORM Community-Based Fathers Survey (B3, B3a)  *also asked on OLLE; will use data from survey with the most complete data	n/a
Parenting Attitudes (toward children)	7 items: frequency of key attitudes (categories, 5-point scale)	nFORM Community-Based Fathers Survey (A3: a-g)  *also asked on OLLE; will use data from survey with the most complete data	n/a

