All in Dads! Healthy Marriage and Responsible
Fatherhood Program Evaluation

Statistical Analysis Plan

NCT05194020

October 17, 2024

1. Data Analysis

Briefly describe the planned approach for data analysis. If an impact analysis is proposed, name the key dependent and independent variables, and describe any methods to minimize Type I error (i.e., finding positive impacts by chance) such as limiting the number of impacts to be analyzed and/or multiple comparison correction. Describe proposed approach(es) for addressing missing data.

Identify study sample

The study sample includes participants who: 1) gave recorded informed consent to be part of the study, and 2) took both an entrance and exit survey (for attitudinal outcomes) or entrance and follow-up survey (for behavioral outcomes). The CONSORT diagram in Figure 2 shows exclusion criteria and the anticipated size of the overall study sample. The analytic sample for particular outcome measures will vary based on missing data.

Defining analysis measures

For each outcome construct, we have identified the relevant measures from nFORM that are theoretically aligned with that construct. We will generate a correlation matrix between items in a given construct to ensure that theoretically related items are also empirically related in our data set. Items that are not strongly correlated with other items in a construct will be removed as necessary. Factor analysis will be used to ensure that all construct items hang together (using an alpha of 0.7 or higher as the threshold). If an alpha of 0.7 cannot be obtained, that outcome will be removed.

Once we are confident that all of the items align with a given construct, we will create a composite measure by taking an average of the scores on each non-missing item in the construct. The measure definition matrix below provides information on each proposed outcome. For composite measures, a change score will be calculated between a participant's pre-program composite score and post-program composite score. For standalone survey items, a change score will be calculated between a participant's pre-survey and post-survey responses.

For the sake of consistency and simplicity, parenting and co-parenting analyses will use a participant's youngest child as the focal child.

Model Specification to Predict Outcomes With Dosage

Construct by Outcome	Dependent Variables (follow-up)	Response Codes for Dependent Variables	Dependent Variable Type	Independent Variables

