Primary outcome:				
Parenting Behavior: 1 item	HOURSFU	# hours spent with child		Dosage: hours of attendance per service
	REACHFU	1 = Almost every day to 5 = never in past month	Continuous	

1 item 11 scaled items Co-parenting Behavior: 11 scaled items	ENGAGFU	1 = never to 5 = every day or almost every day	(using nFORM data); Co-variates: development starting points, risk - family structure, demographics, socioeconomic (ACS & OLLE survey data at baseline)
	COPARFU	1 = strongly disagree to 5 = strongly agree	
		1 = yes, 0 = no	

Secondary outcome:

Parenting Attitudes: 7 scaled items Financial Readiness 1 item 1 item	PATTFU	1 = always to 5 = never	Continuous	Dosage: hours of attendance per service (using nFORM data); Co-variates: development starting points, risk - family structure, demographics, socioeconomic (ACS & OLLE survey data at baseline)
	SAVFU			
	CHECKFU	1 = yes, 0 = no	Dichotomous	

Handling missing data

Outcomes

When creating the composite measures for co-parenting and parenting relationships, we will create a composite score by taking the average of multiple individual items. For these measures, our current plan is to use 20% as a threshold for allowable missing items, based on guidance from evaluation technical assistance resources. This plan is contingent on the final distribution of missing data in our data set. With a 20% threshold, if a respondent is missing more than 1 item used for creating the co-parenting construct or more than 2 items for creating the parenting construct, the respondent will be assigned a missing value for that construct. We will not be imputing truly missing values for outcomes. To create a construct score, the average will divide by the number of non-missing values in the construct.

Participants who have not seen their child within the past month will have their parenting behavior responses set to "Never" (1) and will be included in the analytic sample for that outcome.

For outcomes that use single survey items, participants who do not respond to the item on either the pre- or post-survey will be excluded from the analytic sample for that outcome.

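### Each wave's composite averages only the items answered at that wave, so skipping different items can look like change; the effect on the mean change is probably small, but the SAP does nothing to exclude it

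*SAP*

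**What the plan says.** The SAP (1. Data Analysis, Defining analysis measures) forms a composite by "taking an average of the scores on each non-missing item in the construct". For each father, "a change score will be calculated between a participant's pre-program composite score and post-program composite score". Under Handling missing data, Outcomes, it confirms the denominator ("To create a construct score, the average will divide by the number of non-missing values in the construct") and excludes imputation: "We will not be imputing truly missing values for outcomes".

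The one limit is on how many items may be missing: "our current plan is to use 20% as a threshold for allowable missing items". This is provisional: "This plan is contingent on the final distribution of missing data in our data set". As applied, a composite is set to missing when a respondent is "missing more than 1 item used for creating the co-parenting construct or more than 2 items for creating the parenting construct". The limit is introduced for the co-parenting and parenting relationship composites. Whether it also covers parenting attitudes (R4) is not clear.

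The changes are tested with paired t-tests (SAP, Analytic approach). Neither document requires the same items at both waves, adjusts for differences in item level, or plans a common-item sensitivity analysis.

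**The concern.** Items within a scale usually differ in level: some behaviors are common and others rare. Leaving out a low item raises the mean of the rest, and leaving out a high one lowers it. If a father omits different items at the two waves, or omits an item at one wave only, his change score mixes real change with a change in item set.

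The SAP already applies the paired principle to single-item outcomes, where a father who did not answer at either wave is excluded. Composites have no equivalent rule.

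The engagement part of R1, R2 and R4 are all judged on the mean of such change scores. The study has no control group, so an artefact tied to one wave has nothing to cancel against.

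Two design features make wave-dependent skipping plausible for R1 and R2:
- Protocol 9.1 says the items are asked on both nFORM and OLLE and that the survey with the most complete data will be used. In Protocol 9.3 the only one-year source listed is the OLLE follow-up. Entrance can draw on the better of two sources; follow-up cannot.
- Entrance surveys are proctored by program staff (Protocol 9.3). The follow-up is completed online or by phone with evaluator staff (Protocol 9.5).

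**Working it through.** **The plan's own figure.** The only numbers attached to this rule are the allowed missing items: 1 for co-parenting, 2 for parenting. They do not reproduce from 20%.
- Co-parenting has 11 items (Protocol 9.1: "11 items: frequency of agreement with key co-parenting behaviors (interval, 5-point scale"). 0.20 × 11 = 2.2, so 2 would be allowed; the SAP allows 1.
- Parenting engagement has 7 items in Protocol 9.1. 0.20 × 7 = 1.4, so 1 would be allowed; the SAP allows 2, and 2/7 = 29%.
- The SAP's model table appears to list 11 engagement items, and 2/11 = 18% does fit.

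This mismatch is a separate matter to reconcile. Here it decides which cases are consistent with the 20% threshold: 1 of 11, 1 of 7 and 2 of 11, but not 2 of 7.

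**One father, no true change.** Let k be the items in the scale and m the number skipped.
- Same number skipped at each wave, set A at entrance and set B later: change = (sum of answers in A − sum of answers in B) / (k − m).
- Skipped at the later wave only: change = gap × m/k, where gap is the mean of the remaining items minus the mean of the skipped items.

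Co-parenting example, answers fixed at nine 4s, one 5 and one 1 (total 42):
- Skip the 1 at entrance: 41/10 = 4.10. Skip the 5 later: 37/10 = 3.70. Change = −0.40, the largest size possible with one of 11 skipped at each wave.
- Skip the 1 at entrance only: 42/11 − 4.10 = −0.28.
- If the two skipped answers differ by one point: 1/10 = 0.10 in size.
- If they are equal: exactly 0.

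**Mean change, no true change.** If proportions q1 and q2 of fathers skip the same low item(s) at entrance and at follow-up:

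shift = (q2 − q1) × gap × m/k

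The protocol gives n = 0.70 × 483 = 338 (sections 8.2 and 9.5; using 483 as the base is an assumption). Assumed, because the documents give none of them: change SD 0.7, the skip rates and the gap. SE = 0.7/√338 = 0.0381. Rejection = Φ(−1.96 + shift/SE) + Φ(−1.96 − shift/SE).

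| Skipped | 5% vs 15%, gap 1.0: shift | rejection | 2% vs 22%, gap 1.5: shift | rejection |
|---|---|---|---|---|
| 1 of 11 | 0.10 × 1/11 = 0.009 | 5.7% | 0.30 × 1/11 = 0.027 | 11% |
| 1 of 7 | 0.10 × 1/7 = 0.014 | 6.6% | 0.30 × 1/7 = 0.043 | 20% |
| 2 of 11 | 0.10 × 2/11 = 0.018 | 7.7% | 0.30 × 2/11 = 0.055 | 30% |

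(0.30 = 0.20 × 1.5.) For scale, the change detectable with 80% power at n = 338 is 2.80/√338 = 0.152 SD, or 0.107 points at SD 0.7.

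**Random skipping.** In a simulated no-change population (assumed item means 2.8 to 4.4, 20% of fathers skipping at each wave), the mean change stayed at about 0. The added change-score SD was 0.06 for 1 of 11. This is noise, not bias.

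**Common-item scoring.** If both composites use only items answered at both waves, an unchanging father scores exactly 0 whatever he skips. In simulation with targeted 5% versus 15% skipping, it removed the shift and altered the change-score SD by less than 1%.

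**The case against.** The strongest reply is that averaging available items under a cap is a deliberate choice, with the threshold taken from technical-assistance guidance, and that group-level bias is assumed rather than shown. Bias needs skipping that differs between waves and falls on items of unusual level, and the documents report neither. This stands as a limit on size. It does not repair the rule.

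There are partial safeguards:
- Taking the more complete survey reduces skipping at both waves for R4, but only at entrance for R1 and R2.
- Setting parenting behavior to Never for fathers who have not seen their child removes the artefact where that applies at both waves.
- The correlation and alpha screen checks that items move together. It does not make their means equal.
- The missing-item cap bounds the artefact without removing it, and is itself provisional.

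A reader might go further and infer serious false-positive inflation. Applying the SAP's two missing items to the protocol's 7-item scale gives 0.10 × 2/7 = 0.029 and about 11% rejection in the milder case, and 0.30 × 2/7 = 0.086 and roughly 60% in the stronger one. The documents do not support using these figures: 2 of 7 is 29% missing, above the SAP's own threshold. The stronger case also needs 20 percentage points more fathers to skip the same low items at follow-up, for which there is no evidence.

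A reader might also infer that skipping different items always produces a false change. It does not when the skipped answers balance.

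**Conclusion.** The concern holds as a gap in the scoring rule, of unknown and probably small effect on the group result. The individual artefact follows from the SAP's wording alone. It can reach 0.40 points for co-parenting when one item is skipped at each wave.

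Bias in the mean change is conditional on wave-dependent skipping, which the survey sources make plausible for R1 engagement and R2 but do not establish. Under the moderate assumptions the shift is 0.009 to 0.018 points, well below the 0.107 points detectable with 80% power, and rejection rises from 5% to between 5.7% and 7.7%. It becomes material (11% to 30%) only under skipping that is both strongly unequal and aimed at low items. All of these figures rest on assumed skip rates, item gap and SD. The case for acting is that the remedy is exact and nearly free, not that the results are known to be wrong.

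**What to change.** Add to the SAP under Handling missing data, Outcomes: *The missing-item limit is applied to each wave separately. For a father who meets it at both waves, both composites in his change score are computed on the items he answered at both waves. The change score from all items answered at each wave is reported as a sensitivity analysis.* State whether this and the limit apply to parenting attitudes, and report item-level skip rates by wave.

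The limit should not be moved to the count of common items. A father who skips one different co-parenting item at each wave is kept now and would then be dropped. With 11 items, a limit of one and an assumed 4% random skip rate per item, P(at most 1 missing) is 0.931 per wave, so 0.931² = 87% of fathers are kept. On common items the rate is 1 − 0.96² = 7.84%, and P(at most 1 missing) is 79%.

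The cost is one SAP sentence and a small change in code. Items answered at only one wave are not used in the change score, with negligible loss of precision. Under the stated limits no father is lost: at least 11 − 2 = 9 common co-parenting items remain and, even taking two missing of 7 at each wave, 7 − 4 = 3 engagement items.

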#### 9.4. ENSURING AND MONITORING DATA COLLECTION

*Describe plans for training data collectors and for updating or retraining data collectors about procedures. Detail plans to regularly review data that have been submitted and to assess and swiftly address problems.*

This evaluation will utilize both post-program surveys (completed at the completion of core programming) and follow-up surveys collected one year after enrollment / baseline. The methods for these data collections differ. The primary driver for post-program survey completion is high rates of program retention. This data point will be collected during the last workshop session – after (but during the same session of) the completion of the nFORM post-program data collection. As such only those individuals who complete the program and who are at the data collection session will participate in the post-program data collection.

All program staff and evaluation staff will undergo a rigorous set of trainings to prepare for the evaluation. All staff receive an overview and introductory training to present the goals and objectives of the evaluation effort and its importance to the overall project. Next all staff receive training on human subject's protection and are required to pass a certification test on the subject matter. All staff will also receive a detailed training on the details of the evaluation including the evaluation tools, timing and data collection process.

In addition, the Data Manager and the primary local evaluation staff will undergo a rigorous training process to better understand the context of HMRF research, training on data collection procedures they will be responsible for, and training on the nFORM system and use of nFORM data in a CQI process. MER is creating networks of CQI Data Managers and Evaluation Project Managers across the 12 projects that we are evaluating so that all staff have access to experienced Data Managers and evaluation staff who have done this work previously. This training takes the form of weekly training sessions that are currently under way.

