What steps will be taken to track participants to conduct follow-up surveys with as many participants as possible?	
This evaluation will utilize both post-program surveys, administered after the completion of core programming, and follow-up surveys, collected one year after enrollment/baseline. The data collection methods for the two time periods will differ, and both have been successfully implemented by MER in prior studies.
 
The post-survey data point will be collected during the last workshop session, after the completion of the nFORM post-program data collection, so only those individuals who complete the program and who are at the data collection session will participate in the post-program data collection. Therefore, the primary driver for post-program survey completion is high rates of program retention. The grantee-evaluator joint CQI process will focus on retention as one of the primary areas of program improvement, and as such we are anticipating relatively modest levels of attrition for this data collection.
 
Tracking and data collection for the follow-up survey one year after baseline will be conducted differently, using an intent-to-treat model in which all participants enrolled are included in the follow-up survey data collection process. Participant tracking will begin at enrollment, where detailed tracking information will be collected during the informed consent process. This includes currently available traditional contact information for each participant (address, phone, email), as well as social media contact information (e.g., Facebook, Twitter), and detailed information for secondary contacts who will likely always be in contact with the participant (e.g., parents, siblings, friends). The consent form will obtain permission to contact these secondary sources to locate the participant for follow-up interviews, if necessary. Additionally,
	

\$50 Walmart gift cards are planned as incentives to encourage completion and show respect for the time of the participant.

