Missing data for the implementation outcomes could happen as a result of programmatic data entry issues. For the sake of this evaluation, we assume that any primary or support services received by a participant are being accurately logged into nFORM, so a lack of documented attendance, service contacts, referrals, etc. is indicative of lack of services (i.e., a participant not receiving the program components as intended).

Assessing non-response bias

We will conduct response rate analysis for each primary outcome of interest to assess non-response bias and adjust for threats to internal validity. Using data from the Applicant Characteristics Survey, we will look at demographics (race, ethnicity, age, education level) and primary reason for joining the program among participants who fall into each of the following categories: 1) non-respondents who answered no surveys after the ACS, 2) respondents who completed the pre-survey only, 3) respondents who completed the post-survey only, and 4) respondents who completed both the pre- and post-survey (complete case).

Analytic approach

The main goal of this descriptive study is to assess pre-post change scores in the attitudinal outcomes listed above and assess pre-to-one-year follow-up change scores in the behavioral outcomes listed above among program participants before and after primary workshops. We will use paired sample t-tests to assess the magnitude and significance of changes among program participants in the analytic sample for each outcome. For binary economic stability outcomes, we will descriptively report the percent of participants who opened a checking or savings account one year after enrollment, compared to the percent who had opened these accounts before the program. We will adjust our p-values for multiple hypothesis testing and report the adjusted p-values in the appendix of the final report.

2. Data Archiving and Transfer

Briefly describe the planned approach data arching and transfer by addressing questions below.

What procedures and parameters are established for all aspects of data/information collection necessary to support archiving data collected as part of the evaluation?

Examples include informed consent, data maintenance, de-identifying data procedures.

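### The SAP reads every missing nFORM service record as no service received, although it says entry gaps can occur; this can understate dose and bias the dosage model in a direction the documents cannot fix

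*SAP*

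**What the plan says.** SAP section 1, under the heading on missing data, acknowledges the problem: "Missing data for the implementation outcomes could happen as a result of programmatic data entry issues". It then sets the problem aside by assumption: "we assume that any primary or support services received by a participant are being accurately logged into nFORM". The scoring rule follows: "so a lack of documented attendance, service contacts, referrals, etc. is indicative of lack of services".

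The same section contains a table titled "Model Specification to Predict Outcomes With Dosage". For both primary and secondary outcomes its independent variable is "Dosage: hours of attendance per service", taken from nFORM, with baseline covariates.

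The analytic approach at the end of that section is different: "We will use paired sample t-tests to assess the magnitude and significance of changes among program participants". Account ownership is reported descriptively. Dosage appears in neither, and the SAP does not say how the dosage model will be fitted.

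Two protocol statements decide who can have a recorded dose of zero. On the exit survey, section 9.4 says that "only those individuals who complete the program and who are at the data collection session will participate in the post-program data collection". On the one-year survey, section 9.5 describes "using an intent-to-treat model in which all participants enrolled are included in the follow-up survey data collection process".

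**The concern.** The SAP names a source of error and then adopts a rule that gives a wrong value whenever that error occurs. An unlogged attender and a true non-attender become the same record. Because all enrolled fathers are followed at one year, both kinds may be present in the behavioral analyses, and the file would hold nothing to tell them apart.

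For exit-survey respondents the study holds evidence that could contradict the rule. A father who took that survey was present at the last session, so zero logged workshop hours for him would be visibly wrong. The SAP plans no such comparison and no sensitivity analysis.

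Two results are at stake: the association between hours and outcome, and any description of how much service was delivered, which would be too low.

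**Working it through.** **Inputs.** The documents give no under-logging rate, no distribution of hours and no dosage slope, so there is no planned figure to reproduce. Every rate and distribution below is an assumption. The SAP's sentence is about implementation outcomes; that it also reaches the dosage variable is an inference from both using nFORM service records.

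**A. Whole record lost at random.** Let true dose D have mean m and SD s. Record D\* = D(1 − Z), where Z = 1 with probability q, independent of dose and outcome.

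- Cov(D\*, D) = (1 − q)s²
- Var(D\*) = (1 − q)(s² + m²) − (1 − q)²m² = (1 − q)(s² + q·m²)
- Fitted slope ÷ true slope = s²/(s² + q·m²) = 1/(1 + q/CV²), with CV = s/m

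Example: CV 0.25 and q = 5% give 1/(1 + 0.05/0.0625) = 1/1.8 = 0.56.

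| CV of dose | q = 2% | q = 5% | q = 10% |
|---|---|---|---|
| 0.25 | 0.76 | 0.56 | 0.38 |
| 0.35 | 0.86 | 0.71 | 0.55 |
| 0.50 | 0.93 | 0.83 | 0.71 |
| 1.00 | 0.98 | 0.95 | 0.91 |

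The slope always shrinks here. The amount depends heavily on the assumed CV. These ratios are for an unadjusted slope, whereas the SAP's table includes covariates.

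**B. Single sessions lost at random.** Let sessions attended have mean m and variance V, each unlogged with probability q. The slope ratio is V/((1 − q)V + q·m). The correlation is multiplied by √[(1 − q)V/((1 − q)V + q·m)]. At q = 10%:

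| Mean / SD of sessions | Slope ratio | Correlation factor |
|---|---|---|
| 11 / 1 | 1/(0.9 + 1.1) = 0.50 | 0.67 |
| 9 / 3 | 9/(8.1 + 0.9) = 1.00 | 0.95 |
| 8 / 4 | 16/(14.4 + 0.8) = 1.05 | 0.97 |
| 6 / 4 | 16/(14.4 + 0.6) = 1.07 | 0.98 |

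The slope can halve, stay the same or grow slightly. The correlation falls in every case.

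**C. Whole record lost, related to outcome.** This was simulated with 2,000,000 records, true standardized slope 0.2, dose CV about 0.30 and 10% false zeros overall.

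| False zeros, low-outcome vs high-outcome fathers | Slope ratio |
|---|---|
| 10% vs 10% (random) | 0.46 |
| 15% vs 5% | 0.81 |
| 18% vs 2% | 1.02 |
| 5% vs 15% | 0.12 |
| 2% vs 18% | −0.09 |

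The random row agrees with formula A: 1/(1 + 0.10/0.296²) = 0.47. The other rows show that the bias can vanish or reverse the sign.

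**Reach.** A paired t-test uses only the two scores of each father. No value of q changes it.

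**The case against.** The strongest reply is that the assumption is openly declared and rests on a working process. Protocol section 10 makes the Data Manager chiefly responsible for the quality of staff-entered nFORM data. Section 9.4 has nFORM and OLLE data downloaded every two weeks for review by the CQI team, with dosage among the items tracked, and section 6 gives that team the task of finding and resolving data problems. Section 1.1 of the evaluation plan lists R1 to R4 as outcome questions only, and their paired t-tests ignore dosage.

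Most of this stands. The safeguards lower the likely rate of gaps, and the reach is limited to the dosage model and to descriptions of service delivery. But none of the safeguards is described as matching the log to a second source, and none says what happens to gaps still present at analysis.

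A reader might infer that any dosage association must shrink toward the null. The documents do not support that: it follows only for whole records lost at random, and B and C show other directions. With several per-service doses in one model, error in one can also bias the others either way. A reader might also infer that fathers have in fact been misclassified. No under-logging rate or case is reported, and partial loss gives a low dose rather than zero.

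The remedy has limits too. The protocol does not say that the exit survey is taken face to face, only that respondents are at the session. It describes gift cards as incentives and names no card log; the final card depends on at least 90% attendance, a count that may itself come from nFORM. Neither source can verify support-service contacts or referrals.

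**Conclusion.** The concern holds as a risk of bias in the dosage model and of understated service delivery. It does not touch the paired t-tests for R1 to R4 or the descriptive account percentages. The rule gives a wrong value for any father whose attendance was not entered, and the SAP itself says that such gaps can occur.

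Size cannot be fixed from the documents. If whole records are lost at random, 5% false zeros leave 56% to 95% of the slope for a dose CV between 0.25 and 1.0. Under session-level or outcome-related loss the direction is open. That uncertainty is a reason for a check, since the bias cannot be reported simply as conservative. The conclusion rests on one reading: that the missing-data rule applies to the nFORM hours in the dosage table as well as to the implementation measures it names.

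**What to change.** Replace the rule in SAP section 1 with the following steps, completed before the analysis file is locked:

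1. Match nFORM workshop hours to exit-survey completion. Use gift-card records as a second source only if they are kept independently of nFORM.
2. Where attendance is shown but not logged, correct the log. If it cannot be corrected, set those hours to missing rather than zero.
3. Keep zero only where no other record shows attendance, and flag these zeros as unverified in the analysis file.
4. Report how many fathers were reclassified.
5. Show the dosage model with and without the unverified zeros, including support-service zeros that cannot be cross-checked.

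Step 5 is needed because the match can rescue only fathers who reached the last session; an unlogged father who attended part of the program stays at zero. The exit survey shows presence at that session and not total hours, so gaps in earlier sessions may remain.

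The cost is a record match on survey data already collected, a few SAP sentences, and a few fathers dropped from the dosage model where hours cannot be restored.
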